## **4.2. Endpoints**

### **4.2.1. Primary endpoint**

- The primary lesion is the largest one – based on longitudinal and transverse measurements - and the one to be followed through imaging throughout the duration of the study by taking pictures of the lesion (more details concerning the imaging of the lesions will be addressed in the imaging manual)
- A maximum of 3 lesions – including the primary one – will be thoroughly assessed during the study
- Lesion score (Bates-Jensen Wound Assessment tool [49]) will be performed during Weeks 1, 2, then 4, 6, 8, 10, 12, and EOS (FU) visit. Of note, elements of the Bates-Jensen Wound Assessment tool which imply probing the wound or measuring its depth are left to the discretion of the treating physician at the site and are not compulsory

### **4.2.2. Secondary endpoints**

- Wound infection, both for the primary and the secondary lesions

- Systemic infection
- Surgical treatment of the wound
- Hospitalisation defined as being admitted for >24 hours
- Course of the secondary lesions defined clinically as for the primary [49]
- Change in pain from week 0 to 12 according to 100 mm Visual Analog Pain Scale (VAS)
  - Pain scale done at Screening, weeks 1, 2, 4, 6, 8, 10, 12, and EOS (FU) visit
- Change in dose and type of pain medication assessed as a continuous variable. Name (INN), dose, and number of pills captured.
- Wound QOL score done at Screening and weeks 1, 6, and 12
- Death

#### **4.3. Justification of the Clinical Trial Design**

Preclinical data with SNF472 supports the hypothesis that the compound is able to prevent cardiovascular calcification (CVC). Calciphylaxis is a rare condition with a high mortality rate. It is characterised by progressive painful, necrotic, skin ulcerations, and calcification of blood vessels. It occurs mostly (98% of cases), but not exclusively, in patients with ESRD, where it is also referred to as Calciphic Uremic Arteriopathy (CUA). “Standard of care” of calciphylaxis is not defined by evidence or guidelines. However, experts in the field suggest a personalised management plan, taken from each calciphylaxis patient a personalized selection from a homogenous list of measures to be taken which have recently been summarized [39, 41]. Since there is no standard of care and one-year mortality rates are about 50% -in a year, the study is open-label and has no placebo control arm.

Phase 1 clinical trials with SNF472 have been completed in healthy volunteers and in patients on haemodialysis. The impact of renal failure and the effect of dialysis on the PK of SNF472 have been assessed, both in single and multiple dosing and up to one month of treatment. Calciphylaxis patients are HD patients; hence SNF472 is expected to have the same PK/PD and safety features.

## 5. STUDY POPULATION

The clinical trial population will consist of male or female HD patients diagnosed with CUA, who are 18 years or older. Participants must be able to provide written informed consent and meet all the inclusion criteria and none of the exclusion criteria.

The Investigator will be required to keep a record of patients who were considered for enrolment but not enrolled, e.g., patient screening log, according to local procedures. This information is necessary to establish that the patient population is selected without bias.

### 5.1. Number of Patients

It is planned to include 15 male or female CUA patients who complete the 12-week treatment period.

Patients who leave the clinical trial before being entered into the study will be considered as screening failures and will always be replaced. Therefore, sufficient reserve patients should be recruited, where possible. Patients withdrawn after dosing may be replaced as needed to obtain 15 patients who complete the 12-week treatment period.

See Section 9.5 for a discussion of sample size.

### 5.2. Recruitment

For this study, both non-hospitalised and hospitalised calciphylaxis patients will be recruited after obtaining written informed consent, with a preference for non-hospitalised patients, wherever possible.

Patients will be approached to participate in the study during the Screening period.

### 5.3. Inclusion Criteria

Patients who meet the following criteria will be considered eligible to participate in the clinical trial:

1. Patients with either newly diagnosed CUA OR recurrent CUA that has been dormant with no skin lesion involvement for at least 90 days from study start (new or recurrent diagnosis must be made within 5 weeks of study start)
2. Patients who signed the written informed consent to participate in this clinical trial (prior to any clinical trial-related procedures being performed), after reading the Patient Information Sheet and Informed Consent Form (ICF), and who had the opportunity to discuss the clinical trial with the Investigator or designee
3. Males or females aged  $\geq 18$
4. Patients on maintenance haemodialysis
5. Patients with at least a minimum level of pain on VAS scale or on pain-killers stronger than NSAIDs

6. Females of child-bearing potential should use a highly effective contraceptive measure throughout the study AND have a negative serum pregnancy test at entry. Male patients having sexual relationship in which pregnancy can occur should take adequate contraceptive precautions (wear a condom) (see Section 8.3.1.)

#### 5.4. Exclusion Criteria

Patients who meet one or more of the following criteria will not be considered eligible to participate in the clinical trial:

1. Body weight above 150 kg
2. BMI >35 and central(abdominal) ulcers
3. History of bisphosphonate treatment within 12 months before entering into the study
4. Severely ill patients without reasonable expectation of survival for > 6 months according to the treating physician
5. Patients with scheduled parathyroidectomy during the run-in or study period
6. Female patients who are either intending to get pregnant or are undergoing treatment to get pregnant, as well as breast-feeding females
7. Participation in another clinical trial with an experimental drug within 90 days prior the inclusion
8. Any psychological, emotional problems, any disorders or resultant therapy that is likely to invalidate informed consent, or limit the ability of the patient to comply with the Clinical Trial Protocol requirements
9. Patients who, in the opinion of the Investigator, are considered unsuitable for any other reason

#### 5.5. Patient Withdrawal and Replacement

A patient is defined as having entered the clinical trial when he/she has provided written informed consent. A withdrawal is a patient who receives a study patient code and for whom treatment is prematurely terminated for any reason.

Possible reasons for withdrawal of a subject from the clinical trial:

- Subject does not fulfil inclusion criteria
- AE(s)
- Withdrawal of consent
- Subject lost to follow-up
- Protocol violation
- Pregnancy
- Other reasons as judged by the investigator (see also 7.1.4 12-Lead Electrocardiogram abnormalities)

Patients may withdraw consent for participation in the clinical trial at any time without penalty and for any reason without prejudice to his or her future medical care. The patient does not need to give a reason for withdrawal of consent. The

Investigator is also free to terminate a patient's involvement in the clinical trial at any time, if the patient's clinical condition or non-compliance warrants it. The Sponsor or the Regulatory Authorities may request termination of the clinical trial if there are concerns about study conduct or safety.

In all cases, the reason(s) for withdrawal and the primary reason or failure to provide a reason, must be recorded in the Case Report Form (CRF).

If a patient is withdrawn, or chooses to withdraw, from the clinical trial for any reason, the Investigator must make every possible effort to perform the evaluations described for the End of Study Visit (see Section 8.2.5) or to verify the health status of the patient by calling the national death registry. Withdrawn patients may not re-enter the clinical trial.

Entered patients who leave the clinical trial before receiving a study patient code will be considered as screening failures and will be replaced.

Patients who are withdrawn from the study may be replaced at the discretion of the Sponsor and Principal Investigator. Replaced patients will receive the whole treatment.

All patients who experience a clinically significant AE (in the opinion of the Investigator) which is ongoing either at the time of withdrawal or at the End of Study Visit, will be followed up at appropriate time intervals until the AE is resolved to the satisfaction of the Investigator. Since it is unpredictable how long such a follow-up will take, data from this follow-up generated after study finalization will be recorded by the Investigator in the source documents and reported to the Drug Safety and Pharmacovigilance department, but not necessarily collected in the CRF and the database. However, full details regarding this follow-up will be described in the Clinical Study Report.

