### **8.2.4. Follow-Up Visit W13**

All patients will undergo a physical examination, a 12-lead ECG, and be assessed for resolution of pending AEs and SAEs. In addition, safety laboratory assessments will be performed and the pain and lesion scores will be assessed.

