### **8.2.5. End of Study Visit**

Patients who withdraw consent or are withdrawn from the clinical trial should, if possible, have an End of Study Visit. This visit should take place as soon as possible after the patient has withdrawn consent or has withdrawn from the clinical trial. The assessments and procedures scheduled for the Follow-Up Visit should be performed at the End of Study Visit.

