5.2 Endpoints

5.2.1 Primary endpoint

- The primary endpoint is the absolute change in BWAT total score between baseline (Week 1) and Week 12 for the primary lesion (the largest one).

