6.3.3 Criteria for subject withdrawal

A subject is defined as having entered the clinical trial when he/she has provided written informed consent. A withdrawal is a subject who receives a study subject code and for whom treatment is prematurely terminated for any reason.

Possible reasons for withdrawal of a subject from the clinical trial:

- Adverse Event(s)
- Subject lost to follow-up
- Withdrawal of consent
- Pregnancy
- Death
- Other (specify)

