Missing values (e.g., missing visits, visits with more than 25% of the items missing, or subscales with more than one item missing) will be imputed. Missing imputation will be done on a subscale level. Absolute change from Week 1 to Week 12 will be done using Multiple Imputation, by each subscale and global score and supported by the different sensitivity analysis as specified in Section 8.4. A forest plot summarizing these results will be produced presenting the estimated change from baseline and 95% confidence interval for the different imputation methods (Shell F-1).

Wound Quality of Life was collected at Week 1, Week 6 and Week 12. Differences in percent and absolute change from Week 1 to each visit by each subscale and in the global score will be analyzed using a Paired Student's T-Test (Shell T-7). Means and 95% confidence interval will be presented graphically by visit for the global score and subscales (Shell F-2). This analysis will be done using Observed Cases.

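### Stopping SNF472 counts as leaving the trial, so consenting early stoppers have no scheduled Week 12 assessment and their vital status to Week 13 is not assured

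*Protocol*

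**What the plan says.** Protocol 5.5 defines leaving the trial by the end of treatment: "A withdrawal is a patient who receives a study patient code and for whom treatment is prematurely terminated for any reason". SAP 6.3.3 says the same: "A withdrawal is a subject who receives a study subject code and for whom treatment is prematurely terminated for any reason". Neither document has a status for a patient who is off drug but still on study.

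Protocol 8.2.5 gives these patients, if possible, one End of Study visit, with this instruction on its timing: "This visit should take place as soon as possible after the patient has withdrawn consent or has withdrawn from the clinical trial". On content: "The assessments and procedures scheduled for the Follow-Up Visit should be performed at the End of Study Visit". Protocol 8.2.4 describes the Follow-Up visit as including a physical examination, an ECG and review of open adverse events, and adds that "safety laboratory assessments will be performed and the pain and lesion scores will be assessed". Table 1 also marks images at follow-up. Wound-QoL is not part of that visit. SAP 9.2.2.4 confirms its schedule: "Wound Quality of Life was collected at Week 1, Week 6 and Week 12".

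The endpoint itself is tied to Week 12. SAP 5.2.1: "The primary endpoint is the absolute change in BWAT total score between baseline (Week 1) and Week 12 for the primary lesion". SAP 8.4 handles missing BWAT, VAS and Wound-QoL by multiple imputation, with LOCF and observed cases as sensitivity analyses.

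On deaths, Protocol 5.5 asks for every effort to complete the End of Study evaluations "or to verify the health status of the patient by calling the national death registry". Protocol 7.1.2.4 collects SAEs for 30 days after the last dose unless consent is withdrawn. Protocol 5.5 and 7.1.2.6 follow adverse events that are already open. SAP 9.2.3 takes deaths from the adverse event list (seriousness or outcome) or from the termination reason on the End of Study form.

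**The concern.** A patient may stop SNF472 because of an adverse event, a protocol violation, non-compliance, an ECG finding or clinical condition, and still be willing to be followed. Many will still be on maintenance haemodialysis at the site. Under these rules the trial nevertheless schedules no Week 12 BWAT, VAS, image or Wound-QoL for that patient. The primary-endpoint value is then missing by rule, not by chance.

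Several of the listed reasons for stopping suggest a poorer course. If stoppers do fare worse, an imputation that does not know they stopped will tend to be too favourable, and a single-arm trial has no comparator in which a similar error could offset it. Death is a listed secondary endpoint in a disease whose excess mortality, by Protocol 2.2, is most marked in the first months. A death percentage is hard to read if some dosed patients have unknown status at the end of the period.

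**Working it through.** **The plan's own figure.** Protocol 9.5 gives 15 completers and 80% power for 60% against 25% healed. Type I error is not stated. An exact binomial rule of at least 8 of 15 has a one-sided error of 1.7% and power of 78.7%, so the figure reproduces closely. Follow-up after stopping drug does not change it.

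**Efficacy data available for a patient who stops early and still consents.**
- Before stopping: the scheduled scores to that date.
- At the End of Study visit, if it happens: BWAT, VAS and images, dated near the stop and not at Week 12.
- At Week 12: nothing scheduled.
- Wound-QoL: a patient who stops before Week 6 has only Week 1. LOCF then returns a change of zero; multiple imputation has only the Week 1 value of that patient to work from.

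The imputation model in SAP 8.4 uses the endpoint at all non-missing scheduled weeks and other items of the same scale. It has no term for stopping or for the reason. After the stopper's last score, the trajectory is therefore inferred from that patient's own past and from the patients still observed.

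The Intention to Treat set (SAP 8.2.3.1) needs one post-baseline efficacy measurement. A patient who stops in Week 1 and misses the End of Study visit drops out of it.

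**Coverage of the 30-day SAE window.** Take Week 12 Day 5 as study day 11 × 7 + 5 = 82. A last dose on day d is covered to day d + 30, so the window reaches Week 12 only if d ≥ 82 − 30 = 52, which is Week 8 Day 3. For a last dose on Day 5 of the week shown:

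| Last dose | Study day | SAE collection ends | Days uncovered before day 82 |
|---|---|---|---|
| Week 1 | 5 | 35 | 47 |
| Week 4 | 26 | 56 | 26 |
| Week 6 | 40 | 70 | 12 |
| Week 8 | 54 | 84 | 0 |

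**Illustration of the gap in deaths.** Input: one-year survival of 45% (Protocol 2.2). Assumption: constant hazard.
- Hazard: −ln(0.45)/52 = 0.0154 per week.
- Mortality by 12 weeks: 1 − 0.45^(12/52) = 16.8%, or 0.168 × 15 = 2.5 of 15 patients.
- Last dose 2 weeks after start: window ends at 2 + 30/7 = 6.3 weeks, leaving 6.7 weeks to Week 13. Risk: 1 − 0.45^(6.7/52) = 9.8%.
- Last dose 4 weeks after start: window ends at 8.3 weeks, leaving 4.7 weeks. Risk: 1 − 0.45^(4.7/52) = 7.0%.
- With the one-year mortality of about 50% in Protocol 4.3, the same steps give 1 − 0.50^(6.7/52) = 8.6% and 1 − 0.50^(4.7/52) = 6.1%.

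These risks are for one patient who is alive when SAE collection ends, has no registry check and has no open adverse event under follow-up.

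**The case against.** A reader might infer that deaths after withdrawal are not collected at all. The documents do not support that. A registry route exists, SAEs are collected for 30 days, and open adverse events are followed to resolution; a death as the outcome of such an event is counted under SAP 9.2.3. What remains is narrower: a later death from a new event, or after consent is withdrawn, where no registry check was made. The check is offered as an alternative to the visit, carries no date, and is not among the SAP's sources for deaths.

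A reader might also infer that outcome data end with the drug and that Week 12 values come only from patients who stayed on it. Neither is right. The early visit records lesion, pain and images, and the stopper's own scores inform the imputation. Protocol 9.1.3 even accepted Week 12 or End of Study images, although the SAP replaced that population. Still, an early score is not a Week 12 score. The SAP text between 8.4 and 8.6 was not available for this review; a visit-mapping rule there could relabel an early value but could not supply a Week 12 observation.

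It is tempting to put a number on the BWAT bias. If 3 to 4 of 15 stop and truly do 5 to 10 points worse than imputed, the mean is too favourable by 3/15 × 5 = 1.0 to 4/15 × 10 = 2.7 points. Neither input is in the documents. Patients who die have no Week 12 score that better follow-up could recover. If the 2.5 expected deaths fell among the stoppers, 0.5 to 1.5 patients would remain, and the range would be 0.5/15 × 5 = 0.2 to 1.5/15 × 10 = 1.0.

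The mortality input is probably too high, because exclusion criterion 4 removes severely ill patients not expected to survive 6 months. The zero Wound-QoL change arises only in the LOCF sensitivity analysis, and pulls an average improvement towards no effect. Finally, whether off-drug scores belong in the result is partly a choice of estimand in an exploratory study. That choice is legitimate, but it can be made at analysis only if the scores exist.

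**Conclusion.** The point holds in this form. Both documents treat any premature end of SNF472 as withdrawal, and no section schedules a Week 12 efficacy assessment afterwards for a patient who still consents. The primary endpoint needs that value. The likely direction of error favours the drug, but this rests on the inference that stoppers do worse; the trial documents give no data on it, and the size of the BWAT bias cannot be fixed from them.

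Death ascertainment is partial rather than absent. Vital status to Week 13 is not assured, chiefly for patients whose last dose is before about day 52. The illustrative risk of about 10% or 7% (last dose at Week 2 or Week 4) rests on a constant hazard from 45% one-year survival. The exclusion of patients with short life expectancy pulls it down; the early concentration of deaths described in Protocol 2.2 pulls it up. The change is worth making because it is cheap and because outcomes never observed can only be modelled later.

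**What to change.** - **Protocol 5.5 and 8.2.5, SAP 6.3.3:** define stopping SNF472 and withdrawing consent for follow-up as two separate events.
- **Consenting patients who stop drug:** keep the scheduled BWAT, VAS and image assessments, at minimum at Week 12, and add the Week 12 Wound-QoL.
- **End of Study visit:** add Wound-QoL for patients who leave earlier.
- **Vital status:** replace 'or' with 'and' in Protocol 5.5. Establish vital status at Week 13 for every dosed patient by site contact or the registry already named, subject to consent and local law.
- **SAP 9.2.3:** add that source, and report deaths to Week 13 together with the number of patients whose status is known.

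The rules on when SNF472 is stopped, the dosing and the sample size stay as they are.

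The cost is a short amendment, SAP wording, a few bedside assessments and one status check per patient. SAP 8.6 expects 1 to 2 subjects per site, so the load is small. The real downside is that off-drug scores enter the Week 12 result; an on-treatment summary can be kept as a sensitivity analysis.

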## 6. INVESTIGATIONAL MEDICINAL PRODUCT

### 6.1. Identity of the Investigational Medicinal Products

Information regarding the dosage form, appearance, and manufacturer of the IMP are presented below:

	SNF472																						
Code name:	SNF472																						
Description:	Transparent																						
Presentation:	Liquid																						
Strength:	30 mg/ml or 90 mg/ml																						
Dose:	
Dose will be adjusted by body weight.
 
To simplify logistics, body weights will be divided into 4 body weight categories, in order to homogenise the exposure of patients to the drug. The body weight used to classify the subject into the four categories will be only the dry body weight from the Screening visit.
 
The dose will be as follows:
 
  
 Category	Patient Body Weight Range (kg)	Total Dose (mg) per patient	
   
 1	50	65.9	400	
 
 2	66	80.9	450	
 
 3	81	110.9	700	
 
 4	111	150	900	
  
 
All details of the procedure are described in the Pharmacy Manuals for each concentration.
			Category	Patient Body Weight Range (kg)		Total Dose (mg) per patient	1	50	65.9	400	2	66	80.9	450	3	81	110.9	700	4	111	150	900
Category	Patient Body Weight Range (kg)		Total Dose (mg) per patient																				
1	50	65.9	400																				
2	66	80.9	450																				
3	81	110.9	700																				
4	111	150	900																				

SNF472 will be stored and shipped to either the Pharmacy Services at the Clinical Units or directly to the Clinical Units.

### 6.2. Dose Rationale

The dose selected has a range of 5.6 mg SNF472/kg to 9 mg SNF472/kg depending of subject weight. This dose range was well tolerated in Phase 1 clinical trials (SNFCT2012\_03 and SNFCT2014\_03), and is selected to be the anticipated

therapeutic dose, reaching concentrations to be at the plateau of the PK/PD relationship (see SNFCT2014\_03 CSR). To adjust the dose per kilogram, subjects are divided into 4 body weight categories (see Pharmacy manual for details).

Dose levels of SNF472 from 1 to 20 mg/kg were tested in Phase 1b/2 trials (SNFCT2014\_03) for 1 week and 10 mg/kg for 1 month, without any AE/SAE related with the compound. Cmax values expected at the dose selected are not exceeding (6-fold below) the Cmax of 127,291 ng/mL, which was the NOAEL concentration determined in dog pre-clinical studies.

### **6.3. Supply, Packaging, Labelling and Storage**

The IMP at [REDACTED] B&C will be stored in accordance to with the manufacturer's instructions (-20°C). The IMP will be labelled according to the applicable local health authority, FDA and EMA requirements. [REDACTED] DSM Group will send the IMP to the Clinical Unit. All IMP shipments will be carried out on dry ice.

All supplies of SNF472 must be stored on site at 5°C (±3°C). The preparation of the patient doses will be described in the Pharmacy Manual. There will be two Pharmacy Manuals, one for the 30 mg/ml vials and another for the 90 mg/ml vials. The 30 mg/ml vials are packaged in boxes of 9 vials. The 90 mg/ml vials are packaged in boxes of 3 vials.

